#### **3.3.3 Secondary objectives**

In smokers without previous respiratory disease:

- 1) To evaluate the effectiveness of a multicomponent nutritional educational intervention designed to increase adherence to the MD pattern.
- 2) To study the relationship between lung function and anthropometric parameters such as the abdominal circumference (AbC) and body mass index (BMI).
- 3) To study the relationship between lung function and various markers of food consumption, inflammation and oxidation.

## **4. METHODOLOGY AND WORK PLAN**

### **4.1. DESIGN**

A multicenter, cluster-randomized, controlled clinical trial aimed at assessing the effect on lung function of increasing MD adherence in a cohort of smokers without previous respiratory pathology. (Clinical Trial registry with Nº 000).

Figure 1 shows the flow diagram of the project.

### **4.2. PARTICIPANTS**

The study population will be recruited from patients treated at 20 PCCs managed by the Catalan Institute of Health (ICS) in Tarragona, which provide assistance to an adult population of approximately 280,000 inhabitants.

Participants who give written informed consent to participate and meet the following criteria will be included:

- Active smoker with cumulative consumption  $\geq 10$  pack-years
- Age between 25 and 75 years, inclusive
- Internet access

Participants with any of the following criteria will be excluded:

- History of respiratory disease
- Chronic or terminal disorder that affects basal parameters
- Any limitation to follow-up participation

### **4.3. CALCULATION OF THE SAMPLE**

The sample size was initially calculated for a simple randomized design, using the ARCSINUS approximation. Thus, in a bilateral contrast, accepting a risk  $\alpha = 0.05$ , a risk  $\beta < 0.2$  and a follow-up loss rate of 25%, 192 subjects are required in each group to detect significant differences between two proportions, estimating that this would be 0.17 in group-1 and 0.31 in group-2 [20]. Accepting that the effect of the design is 1.7, applying an intraconglomerate correlation coefficient  $< 0.05$  [23], a sample of 750 participants will be needed, 375 in each group (38 volunteers from each participating PCC).

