## 1. SUMMARY

Recent studies have shown the impact of eating patterns on lung function. However, the specific benefits of the Mediterranean Diet (MD) in preventing pulmonary dysfunction are not well known.

**Objective.** To evaluate the effect of MD adherence on the deterioration of lung function in smokers.

**Methodology.** Design: Controlled, parallel, multicenter, cluster-randomized clinical trial. Participants: 750 active smokers aged 25 to 75 years with a cumulative consumption of more than 10 packets/year, without previous respiratory disease and who agree to the conditions of the study and sign an informed consent to participate. Scope: 20 Primary Care Centers managed by the Catalan Health Institutes in Tarragona Province, to be randomly assigned to a control or an intervention group (1:1). All participants will receive advice to quit smoking. Intervention: A 2-year nutritional intervention designed to increase MD adherence. Elements include: 1) annual visit to deliver personalized nutritional education, 2) annual telephone contact to reinforce the intervention, and 3) access to an ad hoc online dietary blog. Control group: Continuation of usual diet pattern. Assessment (both groups, initially and annually for two years): a) pulmonary function, evaluated by forced spirometry and b) adherence to the MD, evaluated by a 14-item questionnaire and medical tests. Statistical analysis: Intention-to-treat basis, with the individual smoker as unit of analysis. Pulmonary function and adherence to a Mediterranean-style diet in both groups will be compared.

**Expected results.** MD adherence prevents the deterioration of lung function in smokers without previous respiratory disease. Thus, MD is key to pulmonary disease prevention, together with the recommendation of smoking cessation.

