#### **4.4. INTERVENTIONS**

Participating centers will be assigned randomly to a control or intervention group (1:1). Volunteers will be referred to an initial visit (V0) to confirm inclusion criteria and sign an informed consent (Annex 1). Basal variables will be collected at that time.

Participants from the intervention PCCs will enter into an educational program to increase adherence to the MD. It will consist of five contacts that integrate three operational components:

- a) Explain the details of the MD and the benefits of following this dietary pattern in an individual visit of 25-30 minutes (V1). Data on the study variables will be collected and medical tests will be performed. This data gathering will be repeated annually for two years (V3 and V5).
- b) Clarify any doubts about following the MD pattern and other advice received, in a telephone conversation. This annual contact will reinforce the intervention (V2 and V4).
- c) Provide information about MD foods, cooking tips, adapted recipes, and other related topics in an ad hoc nutrition blog.

The control group will carry out the same 5 visits (3 individual visits and 2 phone calls), although no changes will be made in their usual diet and they will not be provided with access to the nutritional blog.

All participants will receive health advice to stop smoking, according to the protocol recommended to health professionals in Catalonia: a proposal of smoking cessation expressed in a clear, firm, and personalized way, in an empathic and respectful setting.

At the end of the study, if the intervention is effective, control group members will be invited to participate in the same intervention program.

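### Section 4.3: 192 per group with a design effect of 1.7 gives 327 per group (654), not the stated 375 (750), and the ICC and cluster size behind 1.7 are not stated

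*Combined protocol and SAP*

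**What the plan says.** Section 4.3 builds the sample size in two steps.

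- **Individual randomisation.** A two-sided 5% test, beta below 0.2, proportions of 0.17 and 0.31, and the arcsine method. The result is stated together with the loss allowance: "a follow-up loss rate of 25%, 192 subjects are required in each group".
- **Clustering.** "Accepting that the effect of the design is 1.7, applying an intraconglomerate correlation coefficient" below 0.05, from which "a sample of 750 participants will be needed, 375 in each group (38 volunteers from each participating PCC").

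Section 4.2 gives the number of clusters: "The study population will be recruited from patients treated at 20 PCCs managed by the Catalan Institute of Health (ICS) in Tarragona". Section 4.4 gives the allocation: "Participating centers will be assigned randomly to a control or intervention group (1:1"). The Summary repeats the total ("Participants: 750 active smokers aged 25 to 75 years") but adds no further step to the calculation.

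**The concern.** The plan presents 750 as the number required, yet its printed inputs do not lead to it. Either 1.7 is not the design effect that was used, or a step is missing. The two cases give 750 different meanings. If 1.7 is right for these centres, 750 includes a margin of about 15%. If the design effect was about 1.95, there is no margin. Section 6 names recruitment as the main limitation, so the sponsor needs to know how far enrolment could fall before the power target is lost.

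The ICC is the second gap. A bound alone does not fix a design effect, because the same ICC gives very different values at different cluster sizes. Without the pair behind 1.7, a reader cannot judge whether it suits this trial's centres.

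**Working it through.** **Inputs.** From 4.3: two-sided alpha 0.05, power 0.80, proportions 0.17 and 0.31, loss 25%, 192 per group, design effect (DE) 1.7, ICC below 0.05, 375 per group, 38 per centre. From 4.2 and 4.4: 20 centres allocated 1:1, so 10 per group.

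**1. The plan's 192 reproduces.**
- h = 2·asin(√0.31) − 2·asin(√0.17) = 0.3310
- n = 2 × ((1.960 + 0.8416)/h)² = 143.3, rounded up to 144 evaluable per group
- 144/0.75 = 192

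So 192 is an enrolled number that already includes the loss.

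**2. The plan's 375 does not reproduce.**
- 192 x 1.7 = 326.4, so 327 per group and 654 in total
- 654/20 = 32.7 per centre, against 38 stated (750/20 = 37.5, rounded up)
- Surplus: 750 − 654 = 96, and 96/654 = 14.7%
- DE needed for 375: 375/192 = 1.953
- Extra allowance needed on top of 1.7: 375/326.4 = 1.149, about 15%

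**3. Other routes to 375, each multiplied by 1.7.**

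| Route | Per group |
|---|---|
| Pooled two-proportion formula (194) | 330 |
| Pooled with continuity correction (212) | 360 |
| Arcsine with continuity correction (209.6) | 356 |
| Loss applied a second time, x 1.25 | 408 |
| Loss applied a second time, /0.75 | 435 |

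None gives 375. One-sided versions of the formulas give smaller numbers.

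**4. What 1.7 implies.** With DE = 1 + (m − 1) × ICC and the printed m = 38:
- DE 1.7 implies ICC = 0.7/37 = 0.019
- ICC 0.05 gives DE = 1 + 37 × 0.05 = 2.85

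Power depends on evaluable participants, 37.5 x 0.75 = 28.125 per centre. At that size DE 1.7 implies ICC = 0.7/27.125 = 0.026.

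**5. Power of 750.** Evaluable per group: 375 x 0.75 = 281.25. The normal approximation is Φ(h·√(281.25/(2·DE)) − 1.96). The last column uses a noncentral t with 18 df (20 centres less 2), which applies only if inference is made at centre level.

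| Case | DE | Normal | 18 df |
|---|---|---|---|
| DE as printed | 1.70 | 85% | 81% |
| DE needed for 375 | 1.95 | 80% | 76% |
| ICC 0.03, m = 28.125 | 1.814 | 83% | 79% |
| ICC 0.04, m = 28.125 | 2.085 | 78% | 73% |
| ICC 0.05, m = 28.125 | 2.356 | 72% | 68% |

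Solving for 80% power gives ICC 0.0355 by the normal approximation (DE 1.963) and 0.028 with 18 df. As a check, 327 enrolled per group (245.25 evaluable) at DE 1.7 gives 80% by the normal approximation, as it should.

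**The case against.** The strongest reply is that the mismatch is in the safe direction. Taking 1.7 at face value, 750 exceeds what is needed by 96, and the gap could be a deliberate margin or generous rounding. That stands as far as it goes: the arithmetic error alone creates no shortfall. But 4.3 mentions no margin and calls 750 the number needed, so the reader cannot tell.

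It is also fair to say that the plan is not silent on clustering. It gives an ICC bound, 38 per centre and 20 centres. What is missing is narrower: the ICC value, and confirmation of the cluster size used for 1.7.

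Three stronger readings are tempting, and the documents support none of them.

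- **That the trial is underpowered.** The plan says the ICC is below 0.05, not equal to it. The 72% figure is therefore a boundary case, and for an ICC up to about 0.035 the target is met by the normal approximation.
- **That the sponsor used particular cluster sizes.** ICC 0.05 with 15 per centre gives 1.70, and with 20 per centre gives 1.95 (192 x 1.95 = 374.4). The plan mentions neither size, so this shows only that such numbers can be found, not what was done.
- **That the 18-df figures are the trial's power.** The Summary specifies "Intention-to-treat basis, with the individual smoker as unit of analysis", and 4.7 does not say how centre enters the model. Those figures are conditional.

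**Conclusion.** Section 4.3 is internally inconsistent. Its printed inputs give 327 per group and 654 in total, not 375 and 750. This part is certain, since the 192 reproduces exactly and no other section supplies a further step.

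The consequence for power is conditional. It rests on proportions of 0.17 and 0.31, 25% loss spread evenly, 20 equal centres and 28.1 evaluable per centre. On that basis beta below 0.2 holds up to an ICC of about 0.035, or about 0.028 with centre-level inference on 18 df. The upper part of the ICC range that the plan accepts therefore misses the plan's own target. Unequal centres would lower power further. For illustration, an assumed coefficient of variation of cluster size of 0.4 gives about 80%, 74% and 69% at ICC 0.03, 0.04 and 0.05 by the normal approximation.

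This should be fixed, but it is not a reason to change enrolment.

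**What to change.** Keep 750 and correct 4.3 so that 192, the design effect and 375 agree. State one of the following, whichever is true:

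- a design effect of 1.7 requires 327 per group (654), and 750 includes a margin; or
- the design effect or additional allowance actually used to reach 375.

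In either case give the ICC value and the cluster size behind the design effect.

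Then state the power of 750 with its assumptions. For example: with 25% loss, 20 equal centres and 28.1 evaluable per centre, power is about 83%, 78% and 72% at ICC 0.03, 0.04 and 0.05 by the normal approximation (about 79%, 73% and 68% if inference is at centre level with 18 df). Claim beta below 0.2 only up to an ICC of about 0.035 (about 0.028 with 18 df). Replacing 1.7 with 1.95 and leaving the power claim unrestricted would not be enough, because 1.95 at 28.1 evaluable per centre corresponds to an ICC of only about 0.035.

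The cost is a text edit with no change in enrolment. The downside is a less favourable stated power near the ICC bound.

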#### **4.4. INTERVENTIONS**

Participating centers will be assigned randomly to a control or intervention group (1:1). Volunteers will be referred to an initial visit (V0) to confirm inclusion criteria and sign an informed consent (Annex 1). Basal variables will be collected at that time.

Participants from the intervention PCCs will enter into an educational program to increase adherence to the MD. It will consist of five contacts that integrate three operational components:

- a) Explain the details of the MD and the benefits of following this dietary pattern in an individual visit of 25-30 minutes (V1). Data on the study variables will be collected and medical tests will be performed. This data gathering will be repeated annually for two years (V3 and V5).
- b) Clarify any doubts about following the MD pattern and other advice received, in a telephone conversation. This annual contact will reinforce the intervention (V2 and V4).
- c) Provide information about MD foods, cooking tips, adapted recipes, and other related topics in an ad hoc nutrition blog.

The control group will carry out the same 5 visits (3 individual visits and 2 phone calls), although no changes will be made in their usual diet and they will not be provided with access to the nutritional blog.

All participants will receive health advice to stop smoking, according to the protocol recommended to health professionals in Catalonia: a proposal of smoking cessation expressed in a clear, firm, and personalized way, in an empathic and respectful setting.

At the end of the study, if the intervention is effective, control group members will be invited to participate in the same intervention program.

#### **4.5. DATA COLLECTION**

All the information will be collected in a computerized data collection questionnaire (DCQ), only accessible from the administrators of the ICS corporate Intranet in Tarragona. Access will be restricted and controlled by a personal password for each researcher, who will be responsible for entering participant data.

This DCQ will include initial information (V0):

- Socio-demographic data (age, sex, marital status, number of children, level of education, social class)
- Medical history and respiratory symptomatology (dyspnea, cough, expectoration, chest pain, other symptoms)

At follow-up visits (V1, V2 and V3), the following information will be obtained:

- Physical examination (weight, height, BMI, blood pressure, and level of exhaled carbon monoxide determined by CO-oximetry)
- Smoking habit (accumulated consumption, current consumption, nicotine dependence, motivation to quit smoking)
- Alcohol consumption
- Physical Activity Classification Questionnaire [24]
- Food frequency questionnaire to assess food consumption [25]
- MD adherence, based on 14-item questionnaire [26]
- 12-lead electrocardiogram
- Forced spirometry and bronchodilator test to measure FVC, FEV and the ratio between them (FEV1/FVC).
- Levels of glucose, total cholesterol and fractions, triglycerides, creatinine and transaminases (serum, autoanalyzer)

- Serum inflammation markers: high-sensitivity C-reactive protein and interleukin-6 (serum, autoanalyzer and assay ELISA)
- Oxidation markers: oxidized LDL in plasma (plasma EDTA, assay ELISA)
- Food consumption markers: excreted of total polyphenols (fresh urine, Folin-Ciocalteau)

#### **4.6. STUDY VARIABLES**

A) The main variable of interest is impaired lung function at the end of follow-up, defined as at least one of the following values: FVC <80%, FEV1 <80%, and FEV1/FVC <0.7 [27]. As secondary variables, spirometry tests (FVC and FEV1), anthropometrics (BMI and AbC), and dietary patterns (adherence and diameter consumption markers) will be evaluated at the end of follow-up.

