#### **3.3.2. Primary objective**

To evaluate the effect of MD adherence on the deterioration of lung function in smokers without previous respiratory disease treated in Tarragona PCCs.

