#### **4.7. STATISTICAL ANALYSIS**

Data will be extracted from the centralized database for blinded analysis, based on intention to treat. The efficacy of randomization will be assessed by comparability and homogeneity of the intervention and control groups. Losses to follow-up will be calculated for each group and evaluated to determine whether the proportion of losses is independent of assignment to the intervention or control group.

Qualitative variables will be described as frequencies or percentages, and quantitative variables by the mean and standard deviation or interquartile range. Analysis will be stratified by study groups and compared at basal level using the  $\chi^2$  test for qualitative and the Student t or Mann-Whitney U test for quantitative variables.

Pulmonary function, anthropometric data, foods consumed, and MD adherence at V1 will be compared to values obtained at the final visit (V5). A multivariate analysis will be performed to determine the factors independently associated with the observed changes, adjusting for relevant covariates. The results will be presented as

hazard ratios, with 95% confidence intervals. All analysis will be performed with the SPSS v22.0 program, considering a p-value <0.05 statistically significant.

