## 6. LIMITATIONS AND STRENGTHS OF THE STUDY

The present study has several limitations. The most important is related to the study population, because inclusion criteria may limit successful recruitment.

The intervention may be less intensive than that described in cardiovascular prevention studies [28]. However, it is an innovative strategy in the prevention of respiratory pathology and its pragmatic design take into account the actual working conditions in daily clinical practice in primary health care. It focuses on reinforcing the consumption of foods considered as protective in the typical diet of the Mediterranean region and reducing the consumption of foods in the standard Western diet that have harmful effects on pulmonary physiology. If the efficacy of this intervention can be demonstrated, it could be readily implemented in clinical practice.

Another limitation to take into account is the knowledge about dietetics and nutrition and the skills of the collaborating health professionals. Knowledge and skills are essential to properly evaluate MD adherence in terms of specific foods, as well as to increase the validity and reliability of the information collected using the study questionnaires and nutritional education. Therefore, in order to standardize the intervention, the dieticians who collaborate in the MEDISTAR study and who design the intervention and develop the educational content and materials will provide thorough training in MD and pulmonary function at the beginning of the study for all participating health professionals.

The effect on lung function will be evaluated by comparing the results of three consecutive forced spirometry measurements, taken annually during the three-year project period. Although this should be sufficient time to allow observations about the longitudinal effect of the diet on spirometry values, it could be too short to show statistically and clinically significant differences between the two study groups. In any case, these results should provide additional evidence of the effect of a MD on lung function in a population of smokers with no previous respiratory disease.

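### The main variable is impairment status at 24 months, not deterioration from baseline, and the spirometry analysis that would measure deterioration is under-specified and inconsistent between sections 4.6, 4.7, 5 and 6

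*Combined protocol and SAP*

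**What the plan says.** - Section 3.3.2 gives the aim: "To evaluate the effect of MD adherence on the deterioration of lung function in smokers without previous respiratory disease".
- Section 4.6 defines the main variable: "The main variable of interest is impaired lung function at the end of follow-up, defined as at least one of the following values", namely "FVC <80%, FEV1 <80%, and FEV1/FVC <0.7". Continuous spirometry comes next in rank: "As secondary variables, spirometry tests (FVC and FEV1", also assessed when follow-up ends. Baseline is not mentioned for either.
- Section 4.2 excludes people by history of respiratory disease. It gives no spirometric entry criterion.
- Section 4.7 describes the comparison: "Pulmonary function, anthropometric data, foods consumed, and MD adherence at V1 will be compared to values obtained at the final visit (V5". A multivariate analysis of the observed changes follows, with covariates not named. The 12-month visit is not mentioned, and neither is centre.
- Section 6 says the effect on lung function will be judged by "comparing the results of three consecutive forced spirometry measurements, taken annually during the three-year project period". It expects the period to be long enough to observe longitudinal effects on spirometry, but adds that "it could be too short to show statistically and clinically significant differences between the two study groups".
- The section 5 schedule marks forced spirometry at V0, V3 (12 months) and V5 (24 months), and not at V1. Section 4.5 lists it under V1, V2 and V3, although V2 is a telephone contact.

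**The concern.** Deterioration is change within a person. Section 3.1 describes it as a gradual loss that smoking accelerates. Status below a cut-off at 24 months differs from this in two ways. It includes impairment already present at entry, which the intervention cannot prevent. It also ignores any slowing of decline in people who do not cross a cut-off.

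Over two years few people will cross. An endpoint that registers only crossings is then a weak instrument for the stated aim, and a null result could be misread as evidence that diet does not slow decline. The analysis that would answer the objective directly, the change in FEV1 compared between arms, is not laid out. The sections also disagree on which spirometries it would use.

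**Working it through.** **1. What each section measures.** Section 3.3.2 asks about change. Section 4.6 measures status at one visit. Section 4.7 uses two visits, the first of which (V1) has no spirometry marked in the schedule. Section 6 uses three annual measurements. These four statements cannot all describe the same analysis. This step needs no assumptions.

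**2. The plan's own figure.** Section 4.3 gives 0.17 v 0.31, two-sided alpha 0.05, beta below 0.2 and 25% loss.
- h = 2·asin(√0.31) − 2·asin(√0.17) = 0.331.
- n = 2(1.960 + 0.842)²/h² = 15.70/0.1096 = 143.3, so 144 per group.
- 144/0.75 = 192, which matches the plan.

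**3. Information kept after dichotomising.** Assume a normal variable with a threshold and no baseline adjustment. The relative efficiency is φ(z)²/[p(1−p)].
- p = 0.17: 0.2531²/0.1411 = 0.45.
- p = 0.31: 0.3528²/0.2139 = 0.58.

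The planned contrast equals a shift of z(0.31) − z(0.17) = −0.496 + 0.954 = 0.458 SD. A continuous 24-month endpoint would need 15.70/0.458² = 74.7, so 75 evaluable per group against 144, before losses and design effect.

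**4. Size of shift the plan needs.** None of these inputs is in the documents: FEV1 as % predicted with mean 88–95 and SD 13–15, predicted FEV1 3.3 L (1 point = 33 mL), and excess decline in smokers of 10–40 mL/year.
- Shift for 31% to 17%: 0.458 × 13 to 0.458 × 15 = 6.0–6.9 points, or 197–227 mL.
- Two years of excess decline: 20–80 mL, or 0.6–2.4 points.
- If the diet abolished all of it, the proportion with FEV1 below 80% would change by about 0.9–5.8 percentage points. The plan assumes 14.

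This models FEV1 alone. The endpoint is any one of three criteria, so the comparison is illustrative.

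**5. Power with the planned sample.** Effective number per arm = 375 × 0.75/1.7 = 165 (section 4.3 inputs as stated).
- Composite at 0.31 v 0.17: about 85%. At 0.31 v 0.25: about 23%.
- Composite at the group's earlier odds ratio of 0.71 (section 3.2), taking 0.31 as the control rate: odds 0.71 × 0.31/0.69 = 0.319, proportion 0.319/1.319 = 0.242, power about 28%.
- Baseline-adjusted FEV1: SE = SD·√(1−ρ²)·√(2/165), with ρ assumed 0.8–0.9. Power is about 9–16% at 0.6 points, 23–49% at 1.2 points and 68–97% at 2.4 points. The shift detectable with 80% power is 1.7–2.8 points (58–91 mL).
- A threshold endpoint starting from 31%, with a shift of 2.4 points: treated proportion Φ(−0.496 − 2.4/SD) = 0.248–0.256, power about 19–24%.

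**6. Value of the 12-month spirometry.** For a linear slope at times 0, 1 and 2 the weights are −½, 0 and +½, so it adds nothing in completers. With 25% lost by 24 months it cuts the variance of the slope difference by about 4–5% if half of those lost attend month 12, and by 8–9% if all do. This held across three assumed variance sets (between-person variance 0.36 L², residual 0.01–0.0225 L², slope 0.0004–0.0025).

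**The case against.** The strongest reply is that impairment is a legitimate, clinically readable endpoint. It rests on a cited spirometry standard, and the hypothesis in section 3.3.1 speaks of preventing impairment. Change is not ignored either: section 4.7 examines changes between visits, and FVC and FEV1 come first among the secondary variables. A continuous primary endpoint is also no cure. Over much of the assumed range (0.6–1.2 points) its power is about 9–49%, so it too could well be null. All of this stands, and it is why replacing the primary endpoint is not called for here.

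It does not remove the mismatch with section 3.3.2, the absence of baseline from the definition, or the missing between-arm specification.

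Four stronger readings are tempting, and the documents do not support them:
- A reader might infer that the 12-month spirometry is discarded. Section 4.7 omits it, but section 6 says three measurements will be compared. This is an inconsistency, and step 6 shows that the value itself adds little beyond cover for losses.
- A reader might take section 6 as conceding that the endpoint will fail. The caveat concerns duration and names no endpoint, and the same sentence calls the period sufficient for longitudinal observation.
- A reader might infer that pre-existing impairment biases the comparison. Random allocation of centres balances it in expectation. The effects are dilution and, with 20 centres, chance imbalance that baseline adjustment would reduce.
- A reader might infer that the earlier odds ratio of 0.71 refutes the planned effect. Its interval (0.28–1.79) contains the planned value, (0.17/0.83)/(0.31/0.69) = 0.46.

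**Conclusion.** The point holds as a mismatch between objective and main variable, together with an under-specified and inconsistent spirometry analysis. The textual part rests on no assumptions: status instead of change, no baseline in the definition, no spirometric exclusion, and sections 4.6, 4.7, 5 and 6 at odds on which measurements count.

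The size is a loss of roughly 42–55% of the information (45–58% kept) if impairment behaves as a cut on a normal variable and baseline is not used. The figures in mL and percentage points rest on assumed FEV1-only inputs and show order of magnitude only.

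The documents do not establish that the trial will be null, or that FEV1 change must be primary. That choice is a trade-off for the sponsor. A well-specified FEV1 analysis, by contrast, is a clear and cheap improvement on a V1-to-V5 comparison.

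**What to change.** In sections 4.6 and 4.7:

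1. Prespecify, as the first (key) secondary analysis, the between-arm difference in FEV1 change to 24 months, with FVC supporting. Use a mixed model on the scheduled baseline, 12-month and 24-month spirometries, with baseline FEV1 in the model and centre as a random effect.
2. Keep the composite as primary if preferred, but adjust it for baseline lung function and account for centre.
3. State which visit supplies the baseline spirometry (V0 or V1) and how the 12-month value is used, so that sections 4.5, 4.7, 5 and 6 agree.
4. State that a null composite at 24 months does not show absence of an effect on deterioration.

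The cost is wording, slightly more analysis work and one more prespecified secondary analysis. No visits, tests or participants are added. If the sponsor chooses FEV1 change as primary, section 4.3 must be restated for a continuous endpoint, with its detectable difference shown, because small effects may remain out of reach.

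### The primary endpoint is impairment status at the last visit, but the plan names no between-arm model for it, does not commit to using baseline lung function, and promises hazard ratios that do not fit

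*Combined protocol and SAP*

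**What the plan says.** **Endpoint.** The hypothesis in Section 3.3.1 is preventive. Section 4.6 defines the main variable as "impaired lung function at the end of follow-up, defined as at least one of the following values", the limits being FVC below 80%, FEV1 below 80% and FEV1/FVC below 0.7. This is a status at the end of the study. It is neither a change nor new impairment. Section 4.3 sizes the trial on proportions of 0.17 and 0.31.

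**Entry.** Section 4.2 excludes "History of respiratory disease", "Chronic or terminal disorder that affects basal parameters", and anything that limits follow-up. No visible criterion refers to a spirometric value. Section 4.4 says "Volunteers will be referred to an initial visit (V0) to confirm inclusion criteria", and the schedule in Section 5 puts forced spirometry at V0, V3 and V5. Figure 1, which covers participant selection, is not shown in the text available.

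**Analysis.** Section 1 says "Pulmonary function and adherence to a Mediterranean-style diet in both groups will be compared", without a method. Section 4.7 names tests for the arms at baseline only. It then sets V1 values against V5 values and adds: "A multivariate analysis will be performed to determine the factors independently associated with the observed changes, adjusting for relevant covariates". Results are to be given as "hazard ratios, with 95% confidence intervals".

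**Baseline visit.** The Section 5 schedule has spirometry at V0 and none at V1. Section 4.5 lists it at V1, and Section 4.7 uses V1 as the starting value.

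**The concern.** The text leaves three analyses open: status at V5, change from baseline, and new impairment. They answer different questions, and without a named model the choice could be made after the data are seen.

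A hazard ratio needs a time to a new event. No event time, censoring rule or survival model is defined. With annual spirometry, onset would be known only to within a year, and participants already impaired would have to be set aside.

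Impairment at entry is a realistic possibility on the plan's own evidence. The planning rates come from the earlier observational study described in Section 3.2. Its title in the reference list says the smokers had no respiratory disease, yet it analysed impaired lung function among them. That label therefore does not exclude impairment. A smoker who enters below a limit and does not change counts as an event in either arm. If the programme works by preventing new impairment, such cases add equally to both arms and shrink the difference. Section 6 already concedes that follow-up may be too short to show one, so a null result would be hard to interpret.

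**Working it through.** **Inputs from Section 4.3:** proportions 0.17 and 0.31, two-sided 0.05, power 80%, 25% loss, arcsine method, design effect 1.7, 375 enrolled per arm. **Not in the documents, so assumed:** the proportion impaired at entry, p0, taken as 0 to 20%.

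**1. The plan's own figure.** h = 2·asin(√0.31) − 2·asin(√0.17) = 0.331. n = 2(1.960 + 0.842)² / 0.331² = 143.3, so 144 completers; 144 / 0.75 = 192 per arm, as stated. (192 × 1.7 = 326, not 375. That is a separate matter, and I use the stated 375.)

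**2. Power with nobody impaired at entry.** Effective completers per arm: 375 × 0.75 / 1.7 = 165. Power = Φ(0.331·√(165.4/2) − 1.960) = 85%.

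**3. Entry cases all persist, and the planned risk ratio (0.17/0.31 = 0.548) acts on new cases only.** The control rate stays at 0.31, and the intervention rate is p0 + 0.548 × (0.31 − p0). The stratified test is a Mantel-Haenszel test by entry impairment, simulated with 165 per arm.

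| p0 | Intervention rate | Power, unadjusted | Power, stratified |
|---|---|---|---|
| 0% | 0.170 | 85% | – |
| 5% | 0.193 | 70% | 77% |
| 10% | 0.215 | 50% | 66% |
| 15% | 0.238 | 31% | 53% |
| 20% | 0.260 | 17% | 38% |

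Hand check at 10%: the entry cases carry no information, which leaves 165.4 × 0.90 = 149 per arm, with rates 0.21/0.90 = 0.233 and 0.548 × 0.233 = 0.128. Then h = 0.277 and power is Φ(0.277·√(149/2) − 1.960), about 66 to 67%.

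The design effect is held at 1.7 throughout. Removing uninformative participants makes the clusters smaller, so the stratified figures are slightly low (about 41% rather than 38% at p0 = 20%).

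**4. Some entry cases revert in both arms (p0 = 10%, control rate still 0.31).** If a quarter revert, power is 60% unadjusted and 67% stratified. If half revert, it is 70% and 72%.

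**5. Everyone shifts by the planned amount.** On a latent normal scale, the distance between 0.17 and 0.31 is 0.954 − 0.496 = 0.458 SD. There is no dilution. Simulated power is about 85% unadjusted, and about 90%, 94% and 98% adjusted at assumed baseline-to-V5 correlations of 0.5, 0.7 and 0.8. One latent variable stands in for the three-part endpoint, so the size of this gain is only indicative.

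**6. New impairment among those unimpaired at entry.** In scenario 3 this has the same power as the stratified test, because the impaired stratum carries no information. If instead 0.17 and 0.31 are the rates among the unimpaired, then at p0 = 10% the end-status rates are 0.10 + 0.90 × 0.17 = 0.253 and 0.10 + 0.90 × 0.31 = 0.379. Power is then about 70% for unadjusted end status and about 82% for the restricted analysis. Under the uniform shift with 5 to 20% impaired at entry, the restricted analysis has about 80 to 93%.

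**The case against.** **Section 4.7 does not commit to an unadjusted test.** It plans a multivariate analysis of change with covariates, and an analysis of change already uses baseline lung function. This stands. A reader might infer from the table that the plan loses a known amount of power. The documents do not support that. They support only that the model is unspecified and that power could be lost under some readings of it.

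**Entry screening may have been intended.** V0 is the selection visit, spirometry is scheduled there, one exclusion concerns disorders that affect baseline parameters, and Figure 1 is missing. If impaired smokers were screened out, the 0% row applies and there is no dilution. This also stands. It is too strong to say that impaired smokers will be enrolled; the visible text merely does not prevent it. Screening would not cure the missing model or the hazard ratio.

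**Randomisation protects the comparison.** Agreed. A reader might infer bias from the entry cases. They are expected equally in both arms, so the issue is power and interpretation.

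**FVC and FEV1 are already secondary variables in Section 4.6.** True, but no baseline-adjusted arm difference is stated for them.

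**Conclusion.** The concern holds as a gap in specification. The effect measure does not match the endpoint or the sample-size basis. No between-arm model is named for the primary endpoint, baseline lung function is not a stated covariate, and the baseline spirometry visit is contradictory.

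The size is conditional on an entry prevalence that the documents do not give. If entry cases persist and the effect falls on new cases only, power drops from 85% to about 50% unadjusted or 66% stratified at 10% impaired, and to 17% or 38% at 20%. Reversion makes the loss smaller, and a uniform shift removes the dilution. Adjustment gained power in every scenario with entry impairment or a uniform shift that was run, though only slightly when half of the entry cases revert.

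A reader might also infer that analysing only participants unimpaired at entry must cost power. Step 6 does not support that: the ranking depends on the mechanism and on what the planning rates describe. That analysis suits a supporting role because it answers a narrower question than the stated endpoint, with no claim about its relative power.

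This should be fixed before analysis. Confidence is high on the wording gap and lower on the magnitude.

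**What to change.** 1. In Section 4.7, specify the primary between-arm model of impairment at V5. It should account for centre, for example by a centre-level analysis of baseline-adjusted residuals, or a mixed model with a small-sample correction for 20 centres. It should adjust for baseline lung function, through entry impairment or baseline spirometry values, without the redundancy of entering FEV1, FVC and their ratio together. Report an odds ratio or risk difference with a 95% confidence interval in place of the hazard ratio.
2. Analyse the secondary FEV1 and FVC at V5 as baseline-adjusted differences between arms.
3. Report new impairment among those unimpaired at entry as a supporting analysis.
4. Reconcile Sections 4.5, 4.7 and the Section 5 schedule on which visit supplies baseline spirometry. State a rule for missing baseline spirometry, so that adjustment does not drop participants from the intention-to-treat set.

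The cost is small. Items 1 to 3 are wording and use spirometry already planned. Item 4 needs one decision on the schedule and one missing-data rule. Enrolment, endpoint, sample size and intention to treat are unchanged.
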